6.4.3.5 Interim Analysis (if applicable)

n/a

6.4.3.6 Health economic evaluation

n/a

6.4.3.7 Other

n/a

6.4.4 Subsets and Covariates

See subject characteristics above 6.4.3.4.

6.4.5 Handling of Missing Data

Missing data will be first attempted to be mitigated by soliciting patient recall through an additional telephone encounter. If information remains missing, this patient will be dropped from further analysis if the missing data is necessary.

7 Trial Administration

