2.2 Background/prevalence of research topic

Gastrointestinal recovery after any visceral surgery is a complex dynamic process with multiple factors ranging from complexity of the surgery, degree of bowel handling and preoperative comorbidities affecting whether the recovery happens over few days, or is a slow prolonged affair lasting weeks.¹ Delays in the gastrointestinal recovery process or ileus is accompanied by distention of the abdomen, pain, nausea, vomiting and the inability to tolerate oral feeding.^{2,3} Interventions to alleviate the ileus/distention include insertion or reinsertion of a nasogastric tube, instating *nil per os* and, if necessitated, parenteral

nutrition.⁴ All of these factors contribute not only to patient discomfort, but extend length of stay (LOS), increase hospital resource utilization and thereby add to overall costs.⁵⁻⁷

Clinically, the markers of gastrointestinal recovery are noted by passage of flatus, defecation and the ability to tolerate solid food without significant nausea and vomiting.⁸ Passage of stool or flatus - considered a surrogate for intestinal and anastomotic continuity - is often used as the trigger to start stepwise dietary orders with the patient's ability to tolerate each step marking their readiness for the subsequent meal. Fast-track and Enhanced Recovery After Surgery (ERAS) programs that promote early feeding in advance of these clinical markers, along with opioid sparing techniques and use of minimally invasive procedures have been shown to be safe and beneficial for many patients by demonstrating earlier recovery and shorter length of stay.⁹⁻¹¹ However, it has also been shown that, for as many as 25% of cases, the strategy does not work as noted earlier, with the need for reinsertion of the nasogastric tube and reinstating nil per os status. In a recent study of 513 consecutive colorectal patients who were on an ERAS protocol, 128 patients (24.7%) needed postoperative reinsertion of nasogastric tube at the 3.9 ± 2.9 postoperative day.⁹ This suggests that, while early postoperative feeding is beneficial to patients in whom recovery is on track, it does not work in cases where patients are not ready for it.

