6.3.6 End of Study and Follow-up

End of study will be discharge of the patient and removal of patches, or early withdrawal by patient or clinician request.

30-days after discharge each patient's electronic medical record will be reviewed for documentation of primary and secondary end points and entered into a REDCap database.

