6.4.3 Planned Analysis

6.4.3.1 Primary Analyses

The primary endpoint is to determine if there is a correlation between the measured motor activity metrics of the various GI organs with measures of recovery, and to mathematically characterize the correlation in a manner that leads to predictive ability. The study is retrospective without intention to treat. Data analysis is performed by the staff of G-Tech Medical located in Mountain View, CA using proprietary software developed specifically for this purpose. Data is accessed on a secure cloud server to which it was uploaded by the mobile app connected to the patches.

Data analysis consists of extracting the myoelectric motor activity measured by the patches in ten-minute time segments and assigning them to an organ or organs. The motor activity at any one time (instantaneous) and the cumulative activity up to that point in time will be examined for correlation to parameters associated with recovery rate such as time to first flatus, time to first solid meal, time to discharge, etc. This will be done across all time points to find the earliest time that offers predictive value. The specific final analysis approach taken will depend on the findings of this pilot study.

In the study² with colonic myoelectric activity measurements after open abdominal surgery an inverse correlation was found between cumulative colon signal strength and time to first flatus which was approximately linear and was best characterized by the root mean square (RMS) deviation of the residuals from a linear fit, in units of hours. The optimal time for this analysis was found to be at 36 hours after surgery.

Similarly in the study¹ with patients undergoing pancreaticoduodenectomy procedure, a correlation was found between cumulative signal strength of the stomach and time to first full meal that was also inverse but not well represented by a linear or other fit. In this case the analysis involved assigning patients to one of two groups, early and late feeders. The stomach activity data were then tested for predictive value against these groups. Patients with stronger signals were more likely to be in the early feeding group and vice versa. A statistical analysis was performed using a receiver-operator characteristic approach that led

pancreaticoduodenectomy for diet “readiness”. American Journal of Physiology-Gastrointestinal and Liver Physiology, 315(5), pp.G743-G751.

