Patient ID # _____

Planned Surgery (pick one)

Enterectomy Only

Right-sided Colectomy

Left-sided Colectomy

Proctectomy

Date of Planned Surgery ___/___/___

ELIGIBILITY

1. Inclusion Criteria (All responses must be “YES” below)

	YES	NO
a. Subject is willing and able to provide informed consent;		
b. Subject is ≥ 18 years of age;		
c. Subject is willing and able to follow all study requirements;		
d. Subject who will undergo or has undergone open or laparoscopic colorectal surgery		

2. Exclusion Criteria (All responses must be “NO” below)

	YES	NO
a. Subject has a known allergy to skin adhesives;		
b. Subject is pregnant or suspects pregnancy;		

2. Informed Consent Obtained

a. Informed Consent Obtained

Y N

2000032548

4/19/22 v1.3

b. Date of Informed Consent ____/____/____

1. Demographics

1. Date of Birth	____	____	/	____	____	/	____	____	____	
	MM	DD		YYYY						
2. Gender		Male		Female						
3. Stated Height	____	Feet	____	Inches						
4. Stated Weight	____	____	____	lbs.						
5. Ethnicity		Caucasian		Black		Hispanic		Asian		Other:

Appendix 3

Recording Procedure and Clinical Markers Case Report Form

Patient ID # _____

Date of Surgery ____ / ____ / ____

Procedure Performed (pick one)

Enterectomy Only

Ostomy Preop? Y N

Right-sided Colectomy

Ostomy post? Y N

Left-sided Colectomy

Proctectomy

POSTOPERATIVE MARKERS

First Flatus Date ____ / ____ / ____

First BM Date ____ / ____ / ____

First Solid Food ____ / ____ / ____

Clinical Ileus (emesis after POD 2, no flatus, reversal of diet order, +/- NGT placed)

Y N

Readmission Y N

Reason for Readmission (choose any)

[] Ileus

[] Dehydration

[] Infection / Anastomotic Leak

[] VTE

[] Unknown

[] Other:

Readmission likely related to surgery? Y N

Appendix 4

Protocol Deviation Form

Date(s) Deviation Occurred:

(If this deviation occurred over multiple days, please indicate entire deviation period)**Associated Study Visit (if applicable):****Type of Deviation**

- Informed consent not properly obtained

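### Section 6.4.5 drops patients known to be flatus-free at last observation together with those whose time was never recorded, which can flatten the predictive slope and understate the RMS error

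*Combined protocol and SAP*

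**What the plan says.** The primary outcome is first flatus (5.2.1). Section 6.4.3.1 relates myoelectric activity to recovery times: "time to first flatus, time to first solid meal, time to discharge, etc". Its colon precedent summarises the fit by the "root mean square (RMS) deviation of the residuals from a linear fit, in units of hours". The same section leaves the final analysis method to depend on what the pilot finds.

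For missing data, 6.4.5 has two steps. The first is "soliciting patient recall through an additional telephone encounter". The second is "If information remains missing, this patient will be dropped from further analysis if the missing data is necessary". No section mentions censoring, a time-to-event or censored regression model, or a sensitivity analysis for missing times.

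On the observation period, 6.3.6 says: "End of study will be discharge of the patient and removal of patches, or early withdrawal by patient or clinician request". It adds that 30 days after discharge each patient's "electronic medical record will be reviewed for documentation of primary and secondary end points". Section 7.5 requires the time of discharge, and the Study Exit Form (Appendix 5) records the date of and reason for exit.

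The Appendix 3 form has a date field for first flatus. The absence of flatus appears only inside a yes/no composite: "Clinical Ileus (emesis after POD 2, no flatus, reversal of diet order, +/- NGT placed".

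**The concern.** A flatus time can be absent for two quite different reasons. Flatus may have occurred without anyone noting when; if that is unrelated to how long it took, dropping the patient costs only precision. Or the patient may have been documented as flatus-free when observation ended. Then the time is known to exceed that point, and the patient is missing because the time is long.

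The second case is foreseeable: study participation ends at discharge or withdrawal, and the ileus item itself anticipates absent flatus. Dropping such patients trims the slow end of the outcome at each level of signal. A linear fit to what remains is generally too flat, and its residuals are too small.

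The stake is the plan's stated aim of a predictive relationship. Slow recoverers are the patients a predictor most needs to get right, and an understated RMS makes its predictions look more precise than they are. The forms do not require anyone to say which of the two cases applies.

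**Working it through.** **Plan's own figure.** There is none to reproduce. The documents give no missing rate, expected correlation or spread of flatus times, and the target of 200 subjects (6.4.2) has no alpha, power or effect size attached.

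**Assumed inputs.** n = 200 (5.3.1). All else is assumption: signal x standard normal; log T = log 48 + 0.5z with z = -0.5x + sqrt(0.75)e, so r = -0.5 on the log scale; log discharge time has SD 0.4 and correlation rho with z. Late means flatus after discharge, set at 10%, or 20 of 200. A share of late times is recovered at random by chart review or recall, and the rest are dropped: 20 with none recovered, 10 with half, 4 with 80%. There were 4,000 simulated trials per cell.

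**Full-data check by formula.** Mean T = 48 x exp(0.125) = 54.4 h. SD = 54.4 x sqrt(exp(0.25) - 1) = 29.0 h. Hours-slope = -0.25 x 54.4 = -13.6 h per SD of signal. Residual RMS = sqrt(29.0² - 13.6²) = 25.6 h, in line with the simulated 25.4-25.5 h.

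**After dropping, 10% late** (ratio to the full-data slope, and RMS in hours):

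| Late times recovered | rho | Log-slope | Hours-slope | RMS (h) |
|---|---|---|---|---|
| 80% | 0.8 | 0.987 | 0.972 | 24.9 |
| 80% | 0 | 0.979 | 0.960 | 24.7 |
| Half | 0.8 | 0.965 | 0.928 | 23.9 |
| Half | 0 | 0.941 | 0.889 | 23.2 |
| None | 0.8 | 0.921 | 0.842 | 22.0 |
| None | 0 | 0.862 | 0.746 | 20.1 |

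Section 2.2 says that delayed recovery goes with a longer stay ("extend length of stay (LOS), increase hospital resource utilization"), which favours the rho = 0.8 rows.

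**If only some missing times are flatus-free cases.** With 20 missing, of whom a quarter were flatus-free at discharge, the log-slope ratio is 0.966 (rho 0.8) to 0.943 (rho 0), a loss of 3-6%. With none flatus-free it is 1.00.

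**Second model.** This is a linear model with a 22 h residual SD (assuming that the ±22 h in 2.1.2 is an RMS), r = -0.6 and an independent end of observation. Dropping the flatus-free 5, 10 or 20% gives slope ratios of 0.93, 0.89 and 0.83, and RMS of 21.2, 20.7 and 20.1 h. Keeping the same patients as right-censored, at n = 200, gives slopes of 1.00, 1.00 and 1.01.

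**When there is no bias, or the other sign.** In that linear model, loss at random or by signal alone gives slope 1.00 and RMS 22.0 h. A contrived case, in which the dropped patients are slow despite high signal, moves the slope away from zero (1.09 to 1.19) while the RMS still falls.

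**Other measures, log-normal model.** With none recovered, power for a correlation at r = -0.3 goes from 99.2% to 96.9-97.7%; at r = -0.5 it stays near 100%. The early/late AUC (split at 48 h) goes from 0.73 to 0.71-0.72 with none recovered and 0.72 with half. It stays at 0.73 if patients event-free past the cut-off are classed as late.

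**The case against.** The strongest reply is that few patients may be affected. Discharge does not end capture of the endpoint: the 30-day chart review and the recall call both follow it, staff prompt app entry daily (6.3.1), and events can be back-logged (6.1.2). The none-recovered rows require chart review and recall to fail every time. This stands, so those rows are an upper bound only.

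The bias is also small against sampling noise. The relative standard error of the log-slope at n = 200 is sqrt(0.75) / (0.5 x sqrt(200)) = 12%; a re-run gave about 15% for the hours-slope and 2.5 h for the RMS. With half recovered and rho = 0.8, the biases are 3.5/12 = 0.3, 7.2/15 = 0.5 and 1.5/2.5 = 0.6 of a standard error. This stands too and limits the severity.

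A third reply is that 6.4.3.1 leaves the method open, so slope and RMS describe a precedent rather than a commitment. That holds for the choice of model. It does not cure the problem, because 6.4.5 removes these patients whichever method is chosen.

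Three stronger readings are tempting, and the documents do not support them:

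- That having some slow recoverers among the dropped is enough for bias. Random or signal-driven loss also removes some, without bias; they must be over-represented at a given signal.
- That the two kinds of missing time can never be told apart afterwards. Chart review, discharge time (7.5) and the exit form may allow partial reconstruction; the forms simply do not require the distinction.
- That a patient missing one time is excluded from every endpoint. The closing qualifier in 6.4.5 can be read as endpoint-specific, so this needs clarifying and is not an established error.

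**Conclusion.** The point holds as a conditional one. The rule in 6.4.5 discards what is known about patients flatus-free at last observation. If slow recoverers are over-represented among those dropped at a given signal, as they are when being flatus-free is the reason a time is missing, the slope is generally flattened and the RMS understated.

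The documents do not show how often this will happen. Under the assumptions above, and with half to 80% of late times recovered, the loss is about 1-6% of the log-slope and 3-11% of the hours-slope, with an RMS of about 25.5 h showing as about 23-25 h. If none are recovered, the upper bound is 8-14%, 16-25% and an RMS of 20-22 h. A reader should not infer that the test for a correlation is compromised: it barely changes. Severity is minor to moderate.

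**What to change.** In 6.4.5 and Appendix 3:

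1. Record the last time the patient was documented flatus-free, and the reason a time is missing.
2. Keep patients known to be event-free at last observation as right-censored at that time, in one pre-specified censored regression or time-to-event model (a log-normal accelerated failure time model with activity as predictor would serve). Show the complete-case fit alongside. In any early/late split, class those event-free past the cut-off as late.
3. State that a patient is excluded only from the endpoint whose time is missing.
4. Report the number of missing times and the reasons.

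The cost is two form fields, a few lines of text and one standard model; discharge time is already collected. The fields are best in place before data collection, since later reconstruction would be partial.

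The drawback is that the censored model assumes non-informative censoring given the signal. If discharge tracks recovery (rho = 0.8, 10% late), it overstates the log-slope by about 4% with no late times recovered, 2% with half and 1% with 80%. That is the opposite direction to the complete-case error, so both fits should be reported. Right-censoring does not help patients whose flatus occurred at an unknown time, or whose signal cannot be interpreted (6.3.7).

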7.1 Ethical Considerations: Informed Consent/Accent and HIPAA Authorization

Declaration of Helsinki

Compliance with the Declaration of Helsinki provides public assurance that the rights, safety, and well-being of trial subjects are protected, and that the clinical trial data are credible.

7.2 Institutional Review Board (IRB) Review

The protocol will be submitted to the IRB for review and approval. Approval of the protocol must be obtained before initiating any research activity. Any change to the protocol or study team will require an approved IRB amendment before implementation. The IRB will determine whether informed consent and HIPAA authorization are required.

The IRB will conduct continuing review at intervals appropriate to the degree of risk, but not less than once per year.

A study closure report will be submitted to the IRB after all research activities have been completed.

Other study events (e.g. data breaches, protocol deviations) will be submitted per Yale's institution's IRB's policies.

7.3 Subject Confidentiality

Subject confidentiality is held in strict trust by the research team. Subject medical record review will be limited to the just the elements needed to complete the study. Only authorized HIPAA and GCP trained study team members will be allowed to extract research data from medical records and enter it into REDCap. No direct subject identifiers will be entered into the data provided to the manufacturer.

Each subject will be assigned a unique study number. A master list linking the unique study number to the human subject will be maintained in a secured Yale Box.com file held by the PI. Each subject will be assigned an alphanumeric character consisting of 4 alpha characters, followed by 3 decimal digits. The 4 alpha characters shall represent the site/institution name. The 3 decimal digits shall start with the number (001) followed by consecutive numbering of all consented study subjects. For example, Yale's third subject consented and enrolled will be numbered:

Y A L E – 0 0 3.

All subjects enrolled will be numbered consecutively even if they are a screen failure. The subjects will be identified as consented, enrolled, and receiving the investigational device in the screening and device accountability log on Yale's REDCap,

7.4 Deviations/Unanticipated Problems

Protocol deviations are not permitted in this study. A protocol deviation is only acceptable if it is to protect the welfare and safety of a subject. A Protocol Deviation Case Report Form will be required to be completed if a protocol deviation occurs.

7.5 Data Collection

Screening, Demographics, and Eligibility Case Report REDCap Form

The Principal Investigator will ensure collection of screening and eligibility data that allows for documentation to show the study subject meets all eligibility criteria and has been properly selected to participate in the study. This can be achieved through a case report form submitted via REDCap. Additionally, demographics and clinical history shall be used to further document the subject's appropriateness for this study and collect the characteristics of the subject that contribute to the analysis of the statistical characteristics of the study population.

Recording Procedure and Clinical Markers Case Report Form

The Principal Investigator will ensure collection of the time of device placement, and the device serial number. The information shall be updated if a new device is used. The Principal Investigator will ensure collection of clinical markers of recovery which at a minimum include time of first flatus, time of first bowel movement, time of first solid meal and time of discharge. These minimum set of inputs should be entered in the G-Tech Patch Monitor App.

7.6 Data Quality Assurance

Data will be stored and collected into two centrally cloud-based locations. Myoelectric signal data and clinical markers of recovery will be fed into G-Tech's centrally managed, deidentified cloud server via the G-Tech Patch Monitor App. Eligibility criteria, clinical history, and 30-day recovery will be abstracted by a member of the study team, input into REDCap with a study tablet, and stored locally at the Yale REDCap instance.

7.7 Study Records

Screening, Eligibility, and Clinical Case Report Form (REDCap)

Informed e-Consent Log (REDCap)

Recording Procedure and Clinical Marker Case Report Form (REDCap)

Protocol Deviation Form (REDCap)

Study Exit Form (REDCap)

Subject ID Log (PI Yale Box.com)

7.8 Access to Source

Myoelectric signal analysis and G-Tech App clinical marker information will be provided back to the PI courtesy of G-Tech. The PI will use the unique identifier to re-link these results to the demographic and clinical characteristic data collected locally and held within REDCap.

7.9 Data or Specimen Storage/Security

All data will be collected in REDCap. Archival logs and analytic datasets derived from the REDCap data will be maintained on a HIPAA-compliant partition of Yale Box.com in a file owned by the PI.

7.10 Retention of Records

Records will be retained up to 3 years to allow for subanalysis as needed.

7.11 Study Monitoring

Study monitoring will be performed by the internal study team with triggers for manufacturer notification and IRB notification as described above in study safety sections.

7.12 Data Safety Monitoring Plan

The risk level of this study is deemed to be low. The device has already received US FDA 510(k) approval and the information collected from patients is not provided back to the treating clinical team.

7.13 Study Modification

Protocol deviations are not permitted. All changes to the study protocol will be submitted as an amendment for review to the Yale IRB.

7.14 Study Discontinuation

Study will be discontinued when meeting its enrollment goal or deemed to be unsafe to proceed after any IRB- or manufacturer-reviewed patient safety event.

7.15 Study Completion

The study is intended to be completed by May 30, 2024. Study completion will be officially recognized with termination documents submitted to the Yale IRB.

7.16 Conflict of Interest Policy

No member of the internal study team maintains a conflicted relationship with the device manufacturer. Any actual conflict of interest of persons who have a role in the design, conduct, analysis, publication, or any aspect of this trial will be disclosed and managed. Furthermore, persons who have a perceived conflict of interest will be required to have such conflicts managed in a way that is appropriate to their participation in the trial. The study leadership in conjunction with the appropriate conflict of interest review committee has established policies and procedures for all study group members to disclose all conflicts of interest and will establish a mechanism for the management of all reported dualities of interest.

All investigators will follow the applicable conflict of interest policies.

7.17 Funding Source

All expenses are supported by internal departmental research startup funds. There is no external source of funding

